The TECNIS Synergy IOL is a one-piece presbyopia-correcting IOL available in non-toric and toric versions that was introduced to the US market in June 2021. At our center, we were the first site in the US to implant the Synergy (June 7, 2021) and have been using the IOL ever since. This Synergy IOL is part of the TECNIS platform, which is composed of time-tested hydrophobic acrylic material with ultraviolet and violet light absorber, 6-mm aspheric optic, refractive index of 1.47, and continuous 360 ° posterior square edge design. The company boasts that the new Synergy IOL combines the benefits from the TECNIS Multifocal and TECNIS Symfony (EDOF) diffractive designs, and that it delivers a wider range of continuous vision and better near vision in day and night than a leading trifocal IOL.¹

To date, there have been only a few investigator-initiated studies that have evaluated the clinical outcomes of the Synergy, but none of these studies have been US-based, nor have they featured a large number of subjects.²⁻⁴

We propose conducting a prospective evaluation of Synergy outcomes that will feature our first 7 months of data collected at our two high-volume, US-based cataract practices. We expect that this analysis will be the first of its kind and will be useful for US cataract surgeons who are considering implementing the Synergy lens in their practice.

1. OBJECTIVE:

To evaluate the visual outcomes in patients with and without astigmatism who underwent uneventful phacoemulsification and bilateral implantation of the TECNIS Synergy IOL.

2. STUDY DESIGN AND METHODS:

- A. **Test article:** Tecnis Synergy Intraocular lens Toric (DFWXXX) and non-toric (DFR00V) using TECNIS Simplicity Delivery System
- B. **Study Design:** Ambispective, multicenter (up to 2 sites in USA), non-therapeutic, single-visit study.
- C. **Subjects:** All consecutive patients who underwent uneventful routine femtosecond assisted laser lens removal and implantation of the Synergy IOL between June 01, 2021 and December 31, 2021 (up to 100 patients) who meet the Inclusion/Exclusion criteria will be enrolled.

1. Inclusion Criteria:

Subjects **MUST** fulfill the following conditions to qualify for enrollment into the trial

1. Age: 18 years and older.
2. Gender: Males and Females.
3. Uneventful bilateral, femtosecond laser assisted lens extraction
4. Bilateral implantation of Synergy IOLs (toric and non-toric) by 5 anterior segment surgeons at Center For Sight ([name], [name], [name], [name], and [name]) and 1 surgeon at Carolina EyeCare Physicians ([name]) through the months of June to December 2021.
5. Willing and able to provide written informed consent for participation in the study.
6. Willing and able to comply with scheduled visit and study examination procedures.
7. Available Macular OCT, IOLMaster700, and Pentacam obtained preoperatively.
8. At least 3 months postoperative from second eye IOL implantation.
9. Postoperative best corrected visual acuity of 0.2 logMAR (20/32 Snellen) or better in both eyes.

2. Exclusion Criteria:

Subjects with **ANY** of the following conditions on the eligibility exam may **NOT** be enrolled into the trial.

1. Established ocular pathology, including: glaucoma (except glaucoma suspects), uveitis, and clinically-significant retinal pathology affecting the macula (with visual acuity worse than 20/32) and/or any other ocular findings that may, in the opinion of the investigator, affect vision.
2. Uncontrolled diabetes.
3. Use of any systemic or topical drug known to interfere with visual performance.
4. Any concurrent infectious/non-infectious conjunctivitis, keratitis or uveitis.
5. Clinically significant corneal dystrophy.
6. Irregular astigmatism.
7. History of chronic intraocular inflammation.
8. Previous intraocular surgery.
9. Previous keratoplasty
10. Previous refractive surgery.
11. Severe dry eye
12. Pupil abnormalities
13. Any clinically significant, serious or severe medical or psychiatric condition that may interfere with the interpretation of study results.
14. Participation in (or current participation) any ophthalmic investigational drug or ophthalmic device trial within the previous 30 days prior to the start date of this trial.
15. Best-corrected distance visual acuity worse than 20/32 in each eye.
16. Inability to focus or fixate for prolonged periods of time (e.g., due to strabismus, nystagmus, etc.)
17. Abnormal iris
18. Patients who had a complication during cataract surgery, which could include ruptured zonules, torn capsule, or vitrectomy.

The principal investigator reserves the right to declare a patient ineligible or non-evaluable based on medical evidence that indicates the patient is unsuitable for the trial.

Additionally, participants who are considered to be a vulnerable subject population are not to be enrolled into the study without prior written authorization from both the Sponsor and the IRB to ensure that a description of additional safeguards are in place during the consenting and enrollment processes. Vulnerable populations include, but are not limited to, the following:

1. Prisoners
2. Nursing home residents /institutionalized individuals
3. Mentally disabled /cognitively impaired individuals
4. Sponsor employees and their family members
5. Site employees and their family members that are directly and indirectly involved with the study
6. Students of the university or the principal investigator participating in the study
7. Economically and/or educationally disadvantaged individuals
8. Comatose individuals / traumatized individuals
9. Adults who do not read and/or write
10. Hearing impaired individuals
11. Terminally ill individuals / individuals with life-threatening conditions

3. Study Procedures

A. Informed Consent / Subject enrollment

Potential subjects will be identified from presenting at the clinic. Additionally, surgery scheduled will be queried to identify patients implanted with the Synergy lens. Once identified as a study candidate, the patient will be asked if he/she would like to participate. The study coordinator or an appropriately trained staff member will answer any and all questions and will obtain informed consent. A copy of the signed informed consent document will be given to the subject. The investigators will be available if the subject wants to discuss further details with him. The patient will understand that participation in the study, or declining to participate, will not affect his/her quality of care.

No subject will be enrolled into the study that does not meet the inclusion/exclusion criteria and does not sign the current approved informed consent document. Informed consent will be obtained prior to collecting any data for the study. The original signed documents will be maintained by the investigator as a permanent part of the subject's research records.

B. Study Visit Schedule and Assessments (Table 1).

1. Visit Schedule:

All subjects enrolled in the study are intended to have undergone uneventful bilateral femtosecond laser assisted cataract surgery with Synergy IOL implantation at least 3 months prior to study visit. Subjects will complete one study visit that can be divided to be completed over two days to accommodate subject fatigue, if necessary.

C. Measurements and evaluations:

Data from routine examination performed prior to the informed consent process may be used to identify potential eligible subjects (e.g., subject chart notes from previous examination documented presence of IOL, and Snellen BCDVA recorded as 20/30 or better in both eyes). However, subject eligibility must be confirmed by collection of new data during the screening and study procedures.

1. Informed consent process will be conducted at this visit. Assessments (Table 1) include:
 - a. Slit lamp examination
 - b. Manifest refraction
 - c. Monocular and binocular uncorrected (UC) and best-corrected distance visual acuity (VA) at 4 m.
 - d. Binocular low contrast (10%) photopic and mesopic BCDVA.
 - e. Binocular UCIVA (at 66 cm), DCIVA (at 66 cm), UCNVA (at 33 and 40 cm), and DCNVA (at 33 and 40 cm) under photopic and mesopic conditions.
 - f. Binocular DC reading speed under photopic and mesopic conditions at 40 cm.
 - g. Pupil size under photopic and mesopic conditions
 - h. Posterior capsule opacification (PCO) evaluation.
 - i. Patient satisfaction, spectacle independence, visual symptoms, and functional vision questionnaires.

All adverse events and complaints will be monitored and recorded at the study visit.

Table 1. Visits and Study Assessments

	Visit 1 Study visit
Informed Consent	X
Inclusion/Exclusion	X
Demographics	X
Manifest refraction – Max Plus	X
UCVA ETDRS (4m)	X*
BCVA ETDRS (4m)	X*
BCVA Photopic low contrast (10%) at 4 m	X**
BCVA Mesopic low contrast (10%) at 4 m	X**
UCIVA ETDRS (66 cm) under photopic conditions	X**
DCIVA ETDRS (66 cm) under photopic conditions	X**
UCNVA ETDRS (40 cm) under photopic conditions	X**
DCNVA ETDRS (40 cm) under photopic conditions	X**
UCNVA ETDRS (33 cm) under photopic conditions	X**
DCNVA ETDRS (33 cm) under photopic conditions	X**
UCIVA ETDRS (66 cm) under mesopic conditions	X**

DCIVA ETDRS (66 cm) under mesopic conditions	X**
UCNVA ETDRS (40 cm) under mesopic conditions	X**
DCNVA ETDRS (40 cm) under mesopic conditions	X**
UCNVA ETDRS (33 cm) under mesopic conditions	X**
DCNVA ETDRS (33 cm) under mesopic conditions	X**
Reading speed at 40 cm under photopic conditions	X**
Reading speed at 40 cm under mesopic conditions	X**
Pupil size under photopic conditions	X
Pupil size under mesopic conditions	X
SLE	X
Dilated fundus exam	X [‡]
Preoperative data (Macular OCT, IOL Master700 and Pentacam)	X [¥]
Intraoperative data (IOL type, IOL power, target refraction, formula used to calculate IOL power, if toric IOL, final axis placement, estimated residual astigmatism and axis)	X
PCO evaluation	X
Toric IOL position	X [‡]
Questionnaires and non-directed complaints	X
AE/Device deficiencies	X

X To be performed as scheduled

* Monocular and binocular testing

** Binocular testing only

[‡] To be performed as deemed necessary by the investigator.

[¥]If available

4. Study endpoint criteria

- A. Patient Completion of Study: If a study patient has completed the study visit, he/she is considered to have completed the study.
- B. Study Completion: The study will be complete when all subjects are enrolled and have completed the study visit.

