5. STATISTICAL CONSIDERATIONS

A. Sample size

As a single-arm study designed to provide normative results for the lens, there is no relevant sample size calculation. Some subgroup analysis is desirable (e.g., toric vs. non-toric, photopic vs. mesopic results, differences by surgeon and/or site). It is expected that 100 subjects (200 eyes) will be sufficient to allow this type of subgroup analysis.

B. Statistical Analysis

All data will be collected by each site and entered into a database. Subjects will be assigned an ID number. Data analysis will be performed without patient identification. Statistical analysis will be performed using standard descriptive statistics and other tests as deemed appropriate based on the characteristics of the data to be analyzed. All statistical tests will be two-sided and interpreted at a 5% significance level. Data analysis will be conducted by a third-party consultant.

C. Study Endpoints:

1. Primary Endpoints:

1. Binocular distance corrected near visual acuity at 40 cm under photopic conditions
2. Binocular distance corrected near visual acuity at 40 cm mesopic conditions

2. Secondary Endpoints:

1. Binocular low contrast distance visual acuity under photopic and mesopic conditions
2. Uncorrected and distance-corrected near (40 cm) visual acuity
3. Uncorrected and distance-corrected intermediate (66 cm) visual acuity
4. Uncorrected and best-corrected distance (4 m) visual acuity
5. Distance-corrected near visual acuity at best distance
6. Non-directed complaints
7. To evaluate patient's overall satisfaction of their vision
8. To evaluate patient's spectacle independence
9. To evaluate visual symptoms using a questionnaire
10. To evaluate the functional vision questionnaire
11. Residual mean spherical equivalent refraction
12. Residual refractive sphere
13. Residual refractive cylinder
14. Percentage of eyes with postoperative MRSE accuracy to target $\leq 0.5D$

D. Safety Analyses

The type, severity, duration and frequency of reported ocular adverse events will be tabulated. Adverse events will also be summarized for events that were considered treatment-related. Comparison of treatment groups with respect to the proportion of study patients reporting adverse events will be made using Fisher's Exact Test.

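### Listed eye conditions still present at the single post-operative visit bar the patient, so they cannot appear in the ocular adverse event table

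*Combined protocol and SAP*

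**What the plan says.** **When exclusions are judged.** The lead-in to the Exclusion Criteria (Section 2.C) says that subjects with any "of the following conditions on the eligibility exam may" not be enrolled. Under Study Procedures, C (Measurements and evaluations), chart data may be used to find candidates, but "subject eligibility must be confirmed by collection of new data during the screening and study procedures".

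**When that exam happens.** Inclusion 8 requires "At least 3 months postoperative from second eye IOL implantation". Study Procedures, B adds: "Subjects will complete one study visit that can be divided to be completed over two days". Table 1 has one visit column. It holds consent, inclusion/exclusion, slit lamp examination, PCO evaluation and the adverse event and device deficiency entry.

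**What is excluded.** Item 4 is "Any concurrent infectious/non-infectious conjunctivitis, keratitis or uveitis". Item 1 lists established pathology, including uveitis, and ends with "and/or any other ocular findings that may, in the opinion of the investigator, affect vision". Items 7, 11, 12 and 17 cover a history of chronic intraocular inflammation, severe dry eye, pupil abnormality and iris abnormality.

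**What is counted.** Study Procedures, C: "All adverse events and complaints will be monitored and recorded at the study visit". Section 5.D: "The type, severity, duration and frequency of reported ocular adverse events will be tabulated". It also plans a separate summary of treatment-related events.

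**The concern.** The same slit lamp finding can do two jobs at this visit. It can make the patient ineligible, and it can be the ocular event that Section 5.D is meant to tabulate. Where it does the first, it never does the second. Uveitis, keratitis, severe dry eye, or a pupil or iris abnormality can each arise after lens surgery, and none of the items on them says that only pre-operative disease counts.

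The protocol describes its subjects as a consecutive series and its results as normative, and it expects them to help surgeons who are considering the lens. A reader would naturally take the adverse event table to describe implanted patients. For the excluded categories it would describe only patients already shown not to have the condition. The plan has no screening log, no count of patients lost to post-operative findings and no caveat on the table.

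**Working it through.** The plan gives no complication rate and says that no sample size calculation is relevant, so there is no planned figure to reproduce. The check is a comparison of timings, followed by a short illustration.

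**Step 1: timing.**
- Exclusions are judged at the eligibility exam (lead-in to the Exclusion Criteria).
- New data must confirm eligibility (Study Procedures, C), and there is one visit (Study Procedures, B; Table 1). The exam is therefore part of that visit.
- Inclusion 8 makes that visit post-operative.
- Adverse events are recorded at that visit (Study Procedures, C; Table 1).

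Eligibility and adverse event recording thus look at the same eyes at the same time.

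**Step 2: item by item.**

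| Item | Limited to pre-operative status? | Other plausible reading |
|---|---|---|
| 4 (conjunctivitis, keratitis, uveitis) | No; worded as concurrent, so it refers to the exam | None apparent |
| 1 (established pathology; open clause on findings affecting vision) | No | Pre-existing disease |
| 7 (history of chronic intraocular inflammation) | No; a history item | Pre-existing disease |
| 11 (severe dry eye) | No | Not stated either way |
| 12 and 17 (pupil, iris) | No | Pre-existing abnormality |
| 8 (earlier intraocular surgery) | No; read literally at this exam it would exclude everyone | Must mean surgery before the lens procedure |

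Item 8 shows that the list mixes pre-operative and visit-time items without marking which is which. Item 4 is the clear case; the others are open to both readings.

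**Step 3: what still reaches the 5.D table.** Item 4 does not bar an episode that resolved before the visit, and non-severe dry eye, visual symptoms and non-directed complaints are not barred by name. However, the plan sets no look-back period or chart source for resolved events.

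**Step 4: illustration.** The planned number is up to 100 patients. For a condition that bars enrolment, the table shows 0/100 at full enrolment.
- Exact two-sided 95% upper limit for 0/100: 1 − 0.025^(1/100) = 3.6%. It is the same for any true rate.
- If such patients were counted, the chance of at least one case among 100 would be 1 − (1 − p)^100. The rate p is an assumption, as the documents give none: 63% at p = 1%, 87% at 2%, 95% at 3% and 99.4% at 5%.
- Adding k such patients to both numerator and denominator gives k/(100 + k). For k = 2: 2/102 = 2.0% (95% CI 0.2% to 6.9%). For k = 5: 5/105 = 4.8% (1.6% to 10.8%). Either would replace 0/100.

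**The case against.** The strongest reply is that the study's stated objective is visual outcomes after uneventful surgery. Both primary endpoints are near acuity, no secondary endpoint is a complication rate, and leaving out eyes with confounding disease is a defensible choice for acuity norms. That stands for the acuity summaries. It does not cover 5.D, which is a planned safety analysis with its own table.

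A second reply is that several items were probably meant as pre-existing disease. That is plausible for items 1, 7, 12 and 17, and item 8 supports it. But the text does not say so, item 4 cannot be read that way, and two sites with six surgeons could apply the list differently.

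Three stronger readings are tempting and are not supported:
- A reader might infer that the whole ocular adverse event table is falsely clean. Only listed conditions that lead to exclusion are lost; the event types in step 3 can still be recorded.
- A reader might infer that eyes with posterior capsule opacification or a displaced lens are excluded. No item names either, and Table 1 schedules PCO evaluation and, where the investigator deems it necessary, toric lens position. They are reached only if an investigator invokes the open clause of item 1.
- A reader might take the 3.6% limit to show serious understatement. Section 5.D plans no confidence interval, so the limit is what a reader would work out from 0/100. At an assumed true rate of 2% or 3% it still covers the truth.

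**Conclusion.** The point holds in a limited form. Under the plan as written, a condition in item 4 that is ongoing at the visit bars the patient and has a count of zero in the 5.D table, whatever its true rate. Items 1, 7, 11, 12 and 17 have the same effect wherever they are applied to status at the visit, which the text allows but does not settle. The bias in the table is downward and favours the lens. Its size cannot be found from the documents, and the rates in the illustration are assumptions.

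This rests on taking the eligibility exam to be part of the single study visit, which the confirmation rule and Table 1 support. It does not make the acuity endpoints invalid for the group enrolled. It does mean that 5.D cannot be read as the frequency of these events in implanted patients.

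**What to change.** 1. For items 1, 4, 7, 8, 11, 12 and 17, state whether each refers to status before the first implantation or at the visit.
2. For any consented patient who fails one of these items because of a condition that began after implantation, record the condition as an ocular adverse event. Include the patient in both the numerator and the denominator of the 5.D table, even if left out of the main acuity summaries. Consent already precedes data collection, so the finding can be recorded at that visit.
3. Report how many of the consecutive implanted patients were excluded for each post-operative finding. This also covers patients passed over at chart review, whom step 2 does not reach. Add a sensitivity summary of the endpoints that includes excluded patients where data were obtained at the visit.
4. State in the report that the acuity results describe a selected group, because inclusion 9 and exclusion 15 still cap acuity after these changes.

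The cost is a wording change, a little more tabulation and probably a slightly less favourable adverse event table. No extra visit or procedure is needed. Because the protocol requires consent before study data are collected, the counts for patients never approached should be agreed with the IRB.

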7. STUDY MONITORING, AUDITING, AND INSPECTING

The nature and location of all source documents will be identified to ensure that original data required to complete the case report forms (CRFs) exist and are accessible for verification by the project manager.

Required examination must be recorded on the CRFs. Provided CRFs can be used as source document. All data reported must have corresponding entries in the source documents. The principal investigator or sub-investigator must review the reported data and certify that the CRFs are accurate and complete. No subject identifiers should be recorded on the CRFs beyond subject number, subject initials and study specific identifiers.

Data from CRFs will be entered into a database provided to each site. Databases will be saved on the site's server. The project manager has access to such server for remote monitoring. Additionally, on-site monitoring visits will be made by the project manager throughout the study.

Upon completion of the CRFs, the data will be reviewed by study manager and statistician for accuracy and completeness. If corrections and/or any additions to the data are deemed necessary, queries will be generated and forwarded to the investigative site. Designated research staff is expected to respond to data queries in a timely manner and ensure that the corrections and changes made to the data in the database are reflected in the subjects' source documentation. Any changes will need to be initialed and dated by the authorized personnel making such changes.

Data will not be sold to third parties. It may be used for future research.

Electronic data will be stored and accessed on a portable device. The laptop is password protected and only the study manager has access to it. Additionally, access to the server requires a user specific password. The database will be password protected when sending to statistician.

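### A patient may be declared non-evaluable on undefined medical evidence, with no time limit, at the unmasked visit that measures the outcomes, and no analysis set or reporting of removals is specified

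*Combined protocol and SAP*

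**What the plan says.** The combined protocol and SAP bears on this point in six places.

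- **Exclusion Criteria, closing paragraph.** The principal investigator "reserves the right to declare a patient ineligible or non-evaluable based on medical evidence that indicates the patient is unsuitable". Neither non-evaluable nor medical evidence is defined. No deadline, second reviewer or record of the decision is required.
- **Exclusion criterion 1.** This adds a judgement-based ground: "any other ocular findings that may, in the opinion of the investigator, affect vision".
- **Section 2.B and Section 3.B.** The design is "Ambispective, multicenter (up to 2 sites in USA), non-therapeutic, single-visit study". The visit may be spread over two days for fatigue, but nothing assigns eligibility to the first day and outcomes to the second.
- **Section 3.C and Table 1.** Earlier chart data may identify candidates, but "subject eligibility must be confirmed by collection of new data during the screening and study procedures". Table 1 puts the inclusion/exclusion check, both primary endpoints, low-contrast acuity, reading speed and the questionnaires in the same visit. Its footnote leaves the dilated fundus exam and the toric IOL position check to the investigator's discretion.
- **Section 4.A.** "If a study patient has completed the study visit, he/she is considered to have completed the study". This defines completion and does not say that completers are analysed.
- **Sections 5 and 7.** Section 5 names the endpoints, descriptive statistics and a third-party analyst. It defines no analysis set and never says what a non-evaluable declaration does to the analysis. Section 7 adds that "The principal investigator or sub-investigator must review the reported data and certify that the CRFs are accurate and complete".

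**The concern.** Ineligible is a status decided at entry. Non-evaluable is a separate status, and it most naturally applies to someone already assessed. Because the power has no time limit and no masking is described, it can be used after the results are known.

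The requirement for medical evidence does not fully close this route, because some of the examinations that could produce such evidence are optional. A patient who reads poorly may be dilated and found to have a subtle macular change. A patient with the same change who reads well may never be dilated. Each removal would rest on a genuine finding and need involve no bad faith, yet removal would still depend on the outcome.

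The study aims to supply normative results from consecutive patients for surgeons considering the lens. Selective loss of poor performers would move the estimates in the lens's favour and shrink the observed SD. A single-arm study has no comparator in which the shift would show.

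**Working it through.** The plan has no figure to reproduce. Section 5.A states that no sample size calculation applies, and no SD, target or expected removal rate is given. The calculation below only illustrates the possible size.

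**Inputs**
- n = 100 subjects (Section 5.A).
- Binocular near acuity at 40 cm, one value per subject, taken as normal (assumed).
- SD 0.10 logMAR (assumed). Shifts scale in proportion to the SD; coverage does not depend on it.
- k = 2, 5 or 10 subjects removed (assumed).

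**Upper bound: exactly the k worst results removed**

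With f = k/n and c = z(1 − f), the large-sample improvement in the mean is φ(c)/(1 − f) SD units. For k = 5, c = 1.645 and φ(c) = 0.1031, so the improvement is 0.1031/0.95 = 0.109 SD. Simulation with n = 100 gives the finite-sample value of 0.106 SD, and 0.106 × 0.10 = 0.011 logMAR. Coverage is the share of simulated samples whose ordinary 95% t-interval contains the true mean.

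| k removed | Mean improves (SD units) | At SD 0.10 (logMAR) | Observed SD / true SD | 95% CI coverage |
|---|---|---|---|---|
| 2 | 0.048 | 0.005 | 0.95 | 91% |
| 5 | 0.106 | 0.011 | 0.90 | 78% |
| 10 | 0.192 | 0.019 | 0.84 | 44% |

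For scale, the 95% CI half-width with all 100 subjects is 1.96/√100 = 0.196 SD, or about 0.020 logMAR. For k = 5, an SD of 0.05 gives a shift of 0.106 × 0.05 = 0.005 logMAR, and an SD of 0.15 gives 0.106 × 0.15 = 0.016 logMAR.

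**Imperfectly targeted removal**

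Here the k subjects removed are those highest on a score that correlates r with near acuity. This is closer to removal on a medical finding.

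| r | k | Mean improves at SD 0.10 (logMAR) | 95% CI coverage |
|---|---|---|---|
| 0.5 | 2 | 0.002 | 94% |
| 0.5 | 5 | 0.005 | 91% |
| 0.3 | 5 | 0.003 | 94% |

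An intermediate case removes 5 subjects at random from the worst 20. The shift is then 0.007 logMAR, with coverage of about 89%.

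**Percentages**

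If 90 of 100 subjects meet some threshold and 5 of the 10 failures are removed, the reported figure rises from 90% to 90/95 = 94.7%.

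**The case against.** Four arguments on the other side have weight.

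1. **The clause does not authorise deletion for a poor score.** A reader might infer that the investigator may simply drop poor results once they are seen. The text does not support that: removal must rest on medical evidence of unsuitability. Nor does anything in the documents show that selective removal was intended or took place. What stands is narrower. The evidence is undefined, and looking for it can be prompted by the outcome.
2. **The context suggests that eligibility is mostly settled early.** The sentence closes a list headed by conditions found at the eligibility exam. Section 3.A bars enrolment of anyone who fails the criteria. Section 3.C lists slit lamp, refraction and distance acuity ahead of the low-contrast, near, reading and questionnaire assessments. This makes early decisions likely, but no order is mandated, and the word non-evaluable reaches beyond enrolment.
3. **There are other safeguards.** Section 7 requires source verification, monitoring and review for completeness. Section 9 requires protocol deviations to be documented with reasons. The analysis is done by a third party. A removal would probably leave a trail, but none of these provisions determines who is analysed or requires removals to be reported.
4. **The large effects need perfect targeting.** Coverage of 44% requires that the ten subjects removed be exactly the ten worst. The primary endpoints have no hypothesis or threshold, so no stated decision would change. This is right, and it is why the worst-case figures are given only as a bound.

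**Conclusion.** The concern holds in a limited form. The plan grants an untimed power to declare patients non-evaluable, places it in the visit that measures the outcomes, leaves some relevant examinations to discretion, and specifies neither an analysis set nor a report of removals. Followed as written, it allows a search for grounds, and then removal, to be triggered by the outcome. That goes beyond a missing detail, because the power itself is stated.

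The possible bias runs from negligible to moderate. With 5 of 100 subjects removed and an assumed SD of 0.10 logMAR, the mean improves by about 0.003 to 0.005 logMAR at correlations of 0.3 to 0.5, with coverage of 94% to 91%. The bound is 0.011 logMAR, with coverage of 78%. The shifts are small in absolute terms; the greater harm is to interval validity and to reported percentages. The SD, the removal counts and the correlations are all assumptions. That the visit is unmasked is inferred from the absence of any masking provision. The point should be corrected, but it does not invalidate the study.

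**What to change.** Make three changes to the text.

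1. **Protocol, after the closing paragraph of the Exclusion Criteria.** Any ineligible or non-evaluable decision is to be made and recorded, with its reason, from chart, slit-lamp, refraction and BCDVA data before low-contrast, intermediate, near, reading and questionnaire testing begins. BCDVA can properly be used here because inclusion criterion 9 already depends on it. The distance-acuity and refraction endpoints are therefore not protected by this step.
2. **Section 5.** Define the analysis set, and list every later removal individually with its reason and its timing relative to outcome testing.
3. **Section 5.** Report both primary endpoints with and without the subjects removed after outcome testing began.

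The paired report is preferable to keeping every consented subject in a single main analysis. The latter would retain subjects later found ineligible, which sits badly with Section 3.A.

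The cost is a few sentences and one extra table. The downside is small: the all-subjects version will include a few subjects with late-found pathology.
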